Our collaborative research with the [tribal name] School revealed that 7.3% and 8.7% of 8-13-year-old [tribal name] youth (only one 13-year-old) reported clinical levels of anxiety and depressive symptoms, respectively, and 5.9% and 2.9% reported subclinical levels.¹⁴ These findings suggest that anxiety and depressive disorder development may be in the early stages and that 8-12-years old may be an optimal age to prevent or mitigate anxiety and depressive symptoms. Moreover, and given the COVID-19 pandemic and restrictions, Native youth from [tribal name] may be a greater risk for anxiety and depression and findings from past pandemics suggest possible long-term effects on AI youths' physical and mental health.^{15,16} Taken together, findings suggests that anxiety and depression are important health concerns that need to be addressed in Native youth and demonstrates a critical need for intervening early with Native youth from [tribal name] to prevent or mitigate anxiety and depressive disorder development.

Brief cognitive-behavioral PEIs have shown to be efficacious in reducing anxiety and depression in non-Native youth.¹⁷⁻²¹ However, there is minimal, though promising, evidence of efficacy to address anxiety and depression in Native youth.²²⁻²⁵ One of the potential barriers to developing an efficacious PEIs for Native youth is the need for culturally grounded adaptation using a community-based participatory research approach, as opposed to traditional cultural adaptation that involves simply minor add-ons of cultural practices and language substitutions (i.e., swapping out an English word with Native words) suggested by cultural experts.²⁶ Our cultural advisory board (CAB) agrees with Indigenous researchers who strongly recommend a culturally grounded adaptions of existing PEIs, including integration of tribal knowledge and ways of thinking, tribal language and associated cultural meaning/context (e.g., the tribal language word for anxiety may mean more than being scared or afraid), cultural beliefs, and healing practices, to enhance fidelity, community ownership, participant buy-in, and intervention effects.^{4,27,28} For example, researchers have emphasized that cultural adaptions of the cognitive-behavioral interventions consider that providers learn to avoid misconstruing reasonable thoughts within the context of the tribal culture as distorted.^{5,28}

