The CAB reviewed potential evidence-based PEIs to adapt. They identified a brief, indicated PEI program for adaption, which is aimed at reducing youth anxiety and stress.^{21,33} They indicated its brevity and potential for youth engagement (board games, playing cards) as appealing. Moreover, it was designed using a CBPR approach and successfully adapted for Latinx youth. There is evidence supporting its feasibility, fidelity, and acceptability with non-Native youth and shown promise in reducing anxiety.^{21,33} It is grounded in cognitive-behavioral and emotional theories of anxiety and stress^{34,35} and aims to improve emotion awareness and expression, reduce cognitive biases, and enhance self-efficacy to manage anxious or stressful situations. It uses streamlined cognitive, behavior, and social skills training using a 12-page manual, active learning (role-playing, games), and brief 30-minute sessions. Training is also minimal at 5 hours plus two 30-minute feedback sessions.

The PEI program^{21,33} is delivered across six weeks with 20-30 min weekly sessions. Youth engage in games and role-play reducing anxiety and stress in mildly challenging situations to provide in-vivo exposure. Session 1 involves introductions, guided relaxation training by

listening to a audio-recording, and learning about different types of emotions using playing cards with characters who display facial emotional expressions. Session 2 teaches youth about worries and how to handle them using a group board game. Session 3 focuses on having conversations with others through guided practice using a role-playing format revolving around different scenarios with the youth. Session 4 teaches youth how to be assertive through guided practice using a role-playing format revolving around different scenarios with the youth. The CAB identified this as an area of adaptation in initial meetings due to the lesson focusing on looking a person in the eye. Session 5 teaches youth how to face their fears by roleplaying mildly fearful situations and learning how to make themselves less scared. Session 6 is a review session. Parents and teachers are sent notes of what youth learned in each session and asked to encourage youth to practice their learned skills.

Purpose of the Study

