At the end of Year 2, the CAB and research team met to review all grouped suggestions gathered from the WGs and FGs. The CAB identified and integrated modifications or additions to our conceptual framework if needed based on the FG feedback. Next, the CAB reviewed the content, format, and learning objectives of each of the six PEI program modules and training protocol within the context of this finalized conceptual model. Specifically, the CAB identified the type of change needed (e.g., content, language, learning strategy), amount of change required (no change, small change, moderate change, large change), and barriers (timeline/budget). The CAB decided on the importance of the change (essential or non-essential), made final decisions on adaptations, and the physical adaptations of the PEI program materials were made by the developers of PEI as requested by the CAB.

Adapted PEI Program Intervention Evaluation (Phase 2; Clinical Trial)

In Year 3, The CAB worked with the research team to culturally adapt the intervention and identified two school counselors (i.e., an American Indian tribal member and a white non-tribal member) to provide it in the schools. Both providers completed the modified PEI program training based on CAB decisions for adaptation and the CITI Training (through Montana State University-Bozeman) before working with youth in the school. They also completed a background check for each school. Providers recorded youth attendance, dropout of the intervention, and completed the Brief Reactions Form for after each session.

In Year 3, we recruited 28 Native youth ages 8-12 years-old from the [two tribal serving school names] (15 youth per school) to participate in the adapted PEI program. The adapted PEI program was delivered to a group of 3-5 youths at one time with three groups participating in each school. Written informed consent was obtained from the parents or legal guardians before youth participated in the intervention or complete pre- and post-survey assessments. Youth participants also provided written assent before completing the pre-intervention and post-intervention surveys or participating in the adapted PEI program.

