Youth participants completed the pre-intervention survey (~30 minutes to complete based on our pilot study) one week before session 1 and the post-intervention survey one week after session 6 of the adapted PEI program. The post-adaptation usability survey was administered at the end of each session. Youth completed the survey using paper and pencil. The research team explained the purpose of the study and intervention. They also read the assent form out loud to youth and answered any questions youth had about the study. Those youth who verbally agreed and checked “yes” on the assent form completed the youth survey and participated in the intervention. Youth who choose not to participate in the study returned to their classroom. All youth were notified of their right to withdraw the study and intervention at any time without consequence. The research team helped youth who may have difficulty comprehending items or response options.

Youth Assessments. The CAB reviewed and approved the following instruments as being culturally appropriate (minor changes were made to existing measures) for our previous study

with 71 Native 8-13-years-old at the [tribal school name]. Each measure showed acceptable to excellent reliability and both convergent and discriminant validity with other established measures in that study (Scott, [name], Small, & McCullen, 2023).

Youth Demographics. We asked children to provide personal information including gender, age, ethnicity, tribal affiliation, grade level, and family structure.

Revised Child Anxiety and Depression Scales – Short Child Version (RCADS-SC).^{37,38} The RCADS-SC is a 25-item self-report instrument used to assess DSM-IV criteria (APA, 1994) of symptoms for anxiety disorders (excluding Posttraumatic Stress Disorder and Specific Phobias) and depression. We asked the children to rate how often each anxiety and depression symptom is true of them on a rating scale consisting of: 1 (Never), 2 (Sometimes), 3 (Often), and 4 (Always). Higher scores represent the experience of more anxiety and depression symptoms as based upon the DSM-IV criteria.

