- B. Confidentiality. We will ensure the steps necessary to ensure confidentiality of the work and focus group discussions and audio recording data. [name] (Project Manager) will inform participants that she cannot guarantee confidentiality of group discussions. However, she will explain to all work/focus groups members the importance of respecting others and maintaining confidentiality of the group discussions. All digitally recorded data gathered from the work and focus groups with tribal community stakeholders (Elders, parents/legal guardians, counselors) and youth will be kept on the Montana State University's Knox password-protected server as an encrypted electronic file. The server is maintained by the university. We will use unique ID code as the file name, which will include the school code, session number, and the recording date. The name of the participant or other identifying information will not be used in the file name. Only trained research staff will have permission to access the Knox folder and review the audio recordings for transcription and analysis.

We also will take the necessary steps to ensure the confidentiality of the survey data. Specifically, we will assign a unique ID number for each youth prior to the administration

of the pre-intervention survey. This unique ID number will only be included with the youth's name on a Master List and will be used as the ID number in the complete deidentified aggregate data file used for study analyses. In addition, only the unique ID number will be present on the surveys. The Master List will contain the unique ID number and the associated youth's name. The Master List with identifying information (i.e., names) and associated unique ID numbers will be kept [name] encrypted and password-protected electronic file on the Montana State University's Knox password-protected server, which is maintained by MSU. [name] will be the only person to have access to the Master List (paper and electronic copy). Additional research staff will not have access to the Master List. The data will only include the unique ID code and no other identifying information.

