American Indian PEI program providers from [tribal school] also will record youth attendance and dropout, which will contain the youth's names. However, the unique ID codes will not be included in this survey and the only information will be the youth's name, attendance (0 = absent, 1 = present) and dropped out of the study (0 = no, 1 = yes). Unlike survey data, [name] will be the only research staff to have access to the attendance and dropout data.

[name] will notify the school counselor and provide the names of youth who report anxiety or depression in the clinical range as compared to their peers at the post-intervention (i.e., T-score > 70 on the Revised Anxiety and Depression Scale). [name] will not provide the actual score and will instruct the school counselor to just talk with the youth about their experiences with anxiety and depression lately. Parents/legal guardians and youth will be informed of this during the informed consent and assent procedures.

C. Cultural Protocols and Tribal/School Policy. [name] and the project manager) will be responsible for working with the Cultural Advisory Board and consultants to ensure the intervention adheres to the cultural protocols and official policies and procedures of the [tribal name], tribal IRB, MSU IRB, and the two tribe-serving schools participating in the study. Tribal Elders (which three Elders serve on the CAB) will be consulted on traditional topics and protocols to follow during data collection and the intervention. We will discuss these cultural protocols, policies, and procedures during the cultural adaptation phase of the study in Year 1 and will revisit in our bi-monthly meetings during Year 2 and 3. We will discuss any problems that are brought to our attention with the CAB until a resolution is achieved.

D. Mandatory Reporting.

All informed consent and assent forms will state that the research team member must report to the proper authorities: (a) there are reports that someone is in immediate physical danger of harming themselves or others, (b) there are indications of child or elder abuse, such that there is physical injury caused by other than accidental means. The project manager will ensure parents/legal guardians, youth, and other adult participants understand this limitation of confidentiality.

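### The counselor notice for RCADS T-scores above 70 is tied to the post-intervention survey alone, so a high baseline score triggers nothing for about seven weeks if sessions are weekly, and possibly never

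*Combined protocol and SAP*

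**What the plan says.** DSMP section 2.B (Confidentiality) provides for the school counselor to receive the names of "youth who report anxiety or depression in the clinical range as compared to their peers at the post-intervention", with the clinical range given as a T-score above 70. The score itself is not passed on, and the counselor is asked only to have a conversation with the youth. Families are to be told of this notice at consent and assent.

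The protocol's Phase 2 section places the youth surveys "one week before session 1 and the post-intervention survey one week after session 6 of the adapted PEI program". The RCADS-SC is in both, because Aim 3 in the SAP is a post-minus-pre change in that scale.

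On linkage, section 2.B says "we will assign a unique ID number for each youth prior to the administration" of the pre-intervention survey. A Master List, open to one person, joins that ID to the name.

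The source program "is delivered across six weeks with 20-30 min weekly sessions". The weekly spacing is not restated for the adapted program.

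**The concern.** The study has chosen a score at which it wants a counselor to speak with a child. It can hold such a score, linkable to a name, before session 1. Yet the rule names only the later survey, and neither the protocol, the DSMP, the SAP nor the IRB letters attach any action to the baseline score or to a missing post score.

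Two consequences follow from the rule as written. A youth above the threshold at baseline waits out the whole program before the score can prompt a conversation. And a youth who was above 70 at baseline but scores 70 or below afterwards, or has no post survey, never triggers the notice. The program may well explain the first of these two cases. It does not explain the second, since the study then has only the baseline score to go on.

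**Working it through.** The plan states no figure on this point, so there is none to reproduce. The steps below size the gap.

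**1. Delay.** Inputs: one week from pre survey to session 1, six sessions, and one week from session 6 to post survey (protocol, Phase 2). Weekly spacing is assumed from the source program. Pre to post = 1 + 5 + 1 = 7 weeks, plus scoring time. With other spacing (assumed), twice-weekly sessions give 1 + 2.5 + 1 = 4.5 weeks and fortnightly sessions give 1 + 10 + 1 = 12 weeks. A baseline notice given by session 2 would come 1 + 1 = 2 weeks after the baseline survey, which is 5 weeks sooner.

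**2. Youth who might be affected.** Inputs: 28 youth recruited (Phase 2). In an earlier local sample, 7.3% and 8.7% "reported clinical levels of anxiety and depressive symptoms, respectively, and 5.9% and 2.9% reported subclinical levels" (Background).
- Full overlap of the two conditions: 28 × 0.087 = 2.4.
- No overlap: 28 × (0.073 + 0.087) = 4.5.
- Chance of at least one such youth: 1 − (1 − 0.073)^28 = 0.88 for anxiety alone, and 1 − (1 − 0.087)^28 = 0.92 for depression alone.

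**3. Precision.** The documents give no counts behind those percentages. I assume 6 of 69 for depression (8.7%) and 11 of 69 for either condition with no overlap (15.9%). Exact (Clopper-Pearson) 95% intervals, multiplied by 28:
- Depression alone: 3.3% to 18.0%, or 0.9 to 5.0 youth.
- Either condition, no overlap: 8.2% to 26.7%, or 2.3 to 7.5 youth.

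The Background does not say that clinical levels meant T above 70, so even the point figures are only a guide.

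**4. High at baseline with no post survey.** No rate of missing post surveys is given. At an assumed 5% to 25%: 2.44 × 0.05 = 0.1 to 4.48 × 0.25 = 1.1 youth.

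**5. What a baseline trigger would add.**
- Extra names, if 30% to 70% of baseline-high youth would be named at post anyway (assumption): 2.44 × 0.3 = 0.7 to 4.48 × 0.7 = 3.1, so about 1 to 3.
- Scoring time at an assumed 5 to 10 minutes a form: 28 × 5/60 = 2.3 hours to 28 × 10/60 = 4.7 hours. Only the 25 RCADS-SC items of 25 + 36 + 10 + 12 = 83 scale items need early scoring.
- Shift in the mean change, if the conversation moved flagged youth by 0.2 to 0.5 SD of the change (assumption): 0.087 × 0.2 = 0.02 SD to 0.160 × 0.5 = 0.08 SD. For comparison, the 95% half-width for the mean change at n = 28 is t(0.975, 27)/√28 = 2.052/5.292 = 0.39 SD.

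**The case against.** The strongest reply is that a post-only check is deliberate. The program is itself a response to anxiety, and a check afterwards finds youth who are still in range. Meanwhile attending youth are not unobserved. The study "identified two school counselors (i.e., an American Indian tribal member and a white non-tribal member) to provide it in the schools", and "The adapted PEI program was delivered to a group of 3-5 youths at one time with three groups participating in each school". Staff record concerns about youth on a form meant for quick review (DSMP section 2), discomfort leads to referral and disclosures are handled (section 3), and a safety board oversees the study (section 5). A reader might infer that a high-scoring child is left without protection for seven weeks. The documents do not support that. What stands against the reply is narrower: those safeguards depend on something seen or said, none uses the score, and nothing says the providers learn it. The plan also gives no reason for the post-only rule.

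A second reply concerns labelling. An indicated program was adapted for universal delivery. Naming high scorers early to a counselor who may also lead their group of three to five partly brings back selection by symptoms, and could change how sessions are delivered. This is a real drawback, and it shapes the recommendation on routing.

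Third, an added contact for the highest baseline scorers falls inside an uncontrolled pre-post change. That also stands. The shift worked out above is small, but it rests on assumed effects, covers the conversation only and not altered delivery, and cannot be separated by any analysis in this design.

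A reader might also infer that youth who drop out will lack a post survey and so be missed. The documents do not say this. The SAP tracks dropout and survey response separately, and nothing states that a youth who leaves the program is not surveyed. The gap is a missing post score, whatever its cause.

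**Conclusion.** The point holds as a gap in a stated rule, worth considering rather than urgent. The text does not use the word only, but the post-intervention survey is the sole trigger named. The consent and assent forms are not in the file, so a baseline notice there cannot be excluded, though the DSMP says they describe the post-intervention one.

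The wording gap is certain and its consequence is less so. The delay is about 7 weeks on the assumption of weekly sessions. The number affected is perhaps 2.4 to 4.5 of 28, with wide intervals on assumed counts and an unconfirmed match between clinical levels and T above 70. Youth with a high baseline score and no post survey would probably number about one or fewer. Nothing in the documents shows that any child was harmed, and the action at stake is a conversation. Recruitment, surveys and change scores are described in the past tense, so for this cohort the point may be closed.

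**What to change.** In DSMP section 2.B, let either the pre-intervention or the post-intervention survey trigger the notice. Keep the cutoff, pass on no score, and keep the instruction that the counselor simply talks with the youth. Have the Master List holder score the baseline RCADS-SC before session 1 or as soon as possible after it. Where possible, send the baseline notice to a counselor who is not that youth's session provider. Amend the consent and assent text through both IRBs, with Cultural Advisory Board input. Keep all youth in the Aim 3 estimate, and report how many were notified at baseline.

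At minimum, use the baseline score for any youth with no post survey, and give the notice after the post-survey window so that it cannot affect the change score. This leaves the delay in place but covers youth whom the present rule cannot reach. If post-only notice is intended for everyone else, state the reason.

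The full change costs more than an edit to one sentence. It needs two IRB amendments, revised forms and about 2 to 5 hours of prompt scoring by one person. The forms are on paper and kept at the university, and the lead before session 1 was cut from two weeks to one (IRB letters of March 23 and February 16, 2024). About 1 to 3 more youth would be named to school staff, with possible labelling, and the small influence on the change score has to be accepted.

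If this cohort's surveys are complete, write the rule into the future efficacy trial that the SAP anticipates, and apply it equally in all arms.
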